Filamentous fungal corneal ulcers continue to have a poor prognosis and further investigation into their treatment is warranted. Unfortunately, *in vitro* collagen CXL alone has failed to demonstrate fungal pathogen inactivation.^{6,12} However, one study showed improved inhibition of fungus *in vitro* with amphotericin plus riboflavin+UV-A compared with amphotericin alone.⁶ The authors suggest that CXL may improve diffusion of antifungal medications or inhibit fungal proliferation through more complex mechanisms. Although the evidence for cross-linking as a treatment for fungal keratitis is less robust, clinicians have already begun using UV-A + riboflavin in conjunction with antifungals in hopes that there will be some benefit in this challenging disease. Thus, scientific investigation into this treatment approach is necessary.

Research Question: Is collagen cross-linking a useful adjuvant in the treatment of infectious corneal ulcers?

1.1 Specific Aims:

- 1. To determine if patients with culture positive bacterial and fungal keratitis clear their repeat cultures more quickly with the addition of collagen cross-linking.
 - We hypothesize that there will be an increased rate of negative cultures immediately post procedure in the CXL group compared with sham CXL.
- 2. To determine if CXL can decrease enzymatic degradation and prevent corneal thinning and perforation.
 - Hypothesis 2A) There will be a decreased rate of perforation among study participants treated with CXL.
 - Hypothesis 2b) There will be less corneal thinning as measured by optical coherence tomography in the CXL group at 3 months.
- 3. To determine what effect CXL has on visual acuity, corneal astigmatism, and 3-month infiltrate/scar size.

- Hypothesis 3A) There will be improved visual acuity with reduced 3-month infiltrate/scar size among study participants treated with CXL.
- Hypothesis 3B) There will be no difference in irregular astigmatism (as measured by topography) between participants in the CXL group versus antibiotics alone.

1.2 Study Outcomes:

Primary Outcome:

- Microbiological cure on repeat culture
 - o CLAIR I. Bacterial ulcers Culture at 4 hours
 - o CLAIR II Fungal ulcers Culture at 24 hours

Secondary Outcomes:

- BSCVA at 3 months
- Scar size/depth, as measured by clinical exam, slit lamp photographs and OCT
- Adverse events including rate of perforation/need for TPK
- Thinning as measured by pachymetry and OCT
- Topography and corneal higher-order aberrations

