3.3 Randomization

Each study eye will be randomly assigned to the treatment group. Block randomization will be performed using a computer program (Statistical package R; Version 2.12; R Foundation for Statistical Computing, Vienna, Austria) by the coordinating site.

Once an eye is enrolled in the study, the study coordinator will assign the study participant's eye an ID (alphanumeric code) and organize the procedure in the operating room within 3 hours for bacterial ulcers, and within 24 hours for fungal ulcers. Once the study participant has been assigned a study participant ID and randomized to treatment group, they will be included in the intention to treat analysis.

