3.4 Study visits

3.3.1 Baseline Visit. During this visit, eligible patients will be enrolled in the study and will give consent. The baseline patient form will be completed and baseline topography will be obtained.

CLAIR I. Bacterial Ulcers:

Study participants will be randomized to one of two possible treatment arms: 1) topical 0.5% moxifloxacin alone 2) topical 0.5% moxifloxacin plus CXL. Those randomized to CXL will undergo the procedure in the operating theatre within 4 hours. Both arms will undergo repeat scraping at 4 hours post enrollment. Thereafter, all study participants will start 0.5% moxifloxacin every hour. All patients will be admitted to the inpatient setting until the 3^{rd} day.

CLAIR II. Fungal Ulcers:

They will be randomized to one of four possible treatment arms 1) topical 5% natamycin alone, 2) topical 5% natamycin plus CXL, 3) topical 0.15% amphotericin alone or 4) topical 0.15% amphotericin plus CXL. All study participants will begin medical therapy immediately (either natamycin or amphotericin) every hour and those randomized to CXL will undergo the procedure in the operating theatre within 24 hours. All study participants will undergo repeat scrapping at 24 hours from enrollment. All patients will be admitted to the inpatient setting until the 3^{rd} day.

- *3.3.2 Procedure visit.* All study participants randomized to CXL will have the procedure in the operating theater. This will occur within 4 hours for bacterial ulcers and within 24 hours of the baseline visit for fungal ulcers. Once a study participant has been randomized to treatment, he will have the treatment even if there is a delay in the operating theatre that results in delayed treatment, however re-scraping will occur at 4 hours for bacterial ulcers and 24 hours for fungal ulcers even if they have not yet had cross-linking. If the cross-linking occurs after repeat scrapping, a third smear and culture should be performed.
- *3.3.3 Day 3 visit.* During this visit, study participants will have BSCVA recorded, IND-VFQ, slit lamp examination and undergo repeat scraping and culture of the corneal ulcer. Thereafter, all additional treatments including but not limited to topical antimicrobials, or oral antimicrobials, will be at the clinician's discretion. At this point patients may be discharged from the inpatient setting.
- 3.3.4 *3 week visit.* During this visit study participants will have BSCVA recorded, slit lamp examination, and they will have digital photography.

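### The cross-linking time limit coincides with the primary scrape, and the SAP's pre/post wording does not tie CLAIR I to the timed culture (minor)

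*Protocol*

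**What the plan says.** - **Primary outcome** (Protocol 1.2): microbiological cure on repeat culture, given as "CLAIR I. Bacterial ulcers Culture at 4 hours" and "CLAIR II Fungal ulcers Culture at 24 hours".
- **Scrape time** (Protocol 3.4, baseline visit): for CLAIR I, "Both arms will undergo repeat scraping at 4 hours post enrollment"; for CLAIR II, "All study participants will undergo repeat scrapping at 24 hours from enrollment".
- **CXL limit** (Protocol 3.4, procedure visit): "This will occur within 4 hours for bacterial ulcers and within 24 hours of the baseline visit for fungal ulcers". Section 4.2.2 repeats the 4 h and 24 h. Neither section says whether the limit applies to the start or the end of the procedure.
- **A different bacterial figure** (Protocol 3.3): the coordinator is to "organize the procedure in the operating room within 3 hours for bacterial ulcers, and within 24 hours for fungal ulcers".
- **Duration** (Protocol 4.2.2): 30 minutes of riboflavin loading, then 30 minutes of UV-A, then transfer to the laboratory for the scrape.
- **Delays** (Protocol 3.4): a randomised participant is treated "even if there is a delay in the operating theatre that results in delayed treatment". The scrape stays at 4 h or 24 h even if CXL has not been done, and a third smear and culture follow if CXL comes after the scrape.
- **Analysis set** (Protocol 3.3): once randomised, "they will be included in the intention to treat analysis".
- **SAP section 2, Specific Aim 1**: the CLAIR I test is described as a paired comparison of cultures before and after cross-linking. The SAP does not mention the third culture.

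**The concern.** The latest permitted time for CXL and the time of the primary scrape are the same instant, while the procedure lasts an hour and is followed by a transfer. If theatre staff treat the limit as a start time, an eye begun in the last hour is within protocol but is scraped untreated or in mid-procedure. Under intention to treat it counts as a CXL eye. Its culture then reflects little or none of the CXL effect, so the contrast shrinks and power is lost for no benefit.

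The second issue concerns which culture is analysed. For a CXL eye scraped on time but before CXL, the timed culture is not a post-cross-linking culture; the third one is. An analyst following the SAP's CLAIR I wording literally could take the third culture for those eyes only. That would break the equal-time comparison, and in the direction that favours CXL.

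**Working it through.** **1. Timing.** CXL lasts 30 + 30 = 60 min (Protocol 4.2.2). To end by the scrape it must start by 4 − 1 = 3 h (CLAIR I) or 24 − 1 = 23 h (CLAIR II), before any allowance for transfer.

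| Limit in the text | Used as a completion limit | Used as a start limit |
|---|---|---|
| CLAIR I, 4 h (3.4, 4.2.2) | ends by 4 h; 0 min for transfer | can end at 5 h, 60 min after the scrape |
| CLAIR I, 3 h (3.3) | ends by 3 h; 60 min left | can end at 4 h; 0 min for transfer |
| CLAIR II, 24 h (3.3, 3.4, 4.2.2) | ends by 24 h; 0 min for transfer | can end at 25 h, 60 min after the scrape |

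**2. The SAP's sample sizes.** The SAP gives 80% versus 50% culture-positive, α = 0.05 with N = 78 (CLAIR I) and α = 0.0125 with N = 110 (CLAIR II). It states no power. For a two-sided pooled-variance test of two proportions,

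n per group = [z(1−α/2)·√(2p̄(1−p̄)) + z(power)·√(p₁(1−p₁) + p₂(1−p₂))]² / (p₁−p₂)²

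With p₁ = 0.80, p₂ = 0.50 and p̄ = 0.65, the two roots are √0.455 = 0.6745 and √0.41 = 0.6403. At 80% power:

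- CLAIR I: (1.9600 × 0.6745 + 0.8416 × 0.6403)² / 0.09 = 38.5, so 39 per arm and 78 in total.
- CLAIR II: (2.4977 × 0.6745 + 0.8416 × 0.6403)² / 0.09 = 54.9, so 55 per group and 110 in total.

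Both totals are reproduced, so two-sided 80% power is a reasonable inference. For CLAIR II this means 55 versus 55, that is, CXL against no CXL pooled over the two antifungals. At the rounded sizes the power is 80.5% (CLAIR I) and 80.1% (CLAIR II).

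**3. Dilution.** Let d be the share of CXL eyes scraped before CXL is complete, and suppose that these eyes show no effect (worst case). Then p₂ = 0.50 + 0.30d, and

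power = Φ{[(p₁−p₂)√n − z(1−α/2)·√(2p̄(1−p̄))] / √(p₁(1−p₁) + p₂(1−p₂))}

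The documents do not give d. One illustration for CLAIR II: if the limit is a start limit and starts are spread evenly over 24 h, the last hour holds d = 1/24 = 4.2%, or 55/24 ≈ 2.3 eyes. Then p₂ = 0.5125, the difference is 0.2875, and power = Φ[(0.2875 × 7.4162 − 2.4977 × 0.6717)/0.6402] = Φ(0.710) = 76.1%. If those eyes keep half the effect (p₂ = 0.50625), power is 78.1%.

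| d | CLAIR I power (39 vs 39) | CLAIR II power (55 vs 55) |
|---|---|---|
| 0 | 80.5% | 80.1% |
| 5% | 76.6% | 75.3% |
| 10% | 72.3% | 70.0% |

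For CLAIR I with theatre start by 3 h, 3 h + 60 min = 4 h, so d = 0 and nothing is lost apart from the missing transfer time.

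**4. Which culture.** Under Protocol 3.4 the order for a delayed CLAIR I eye is: enrolment, scrape at 4 h, hourly moxifloxacin from then on, CXL, third scrape. A control eye contributes its 4 h culture, taken before moxifloxacin. The third culture therefore follows antibiotic treatment and one extra scrape. SAP section 2 itself puts the effect of a repeat scrape at about an 8% reduction in positivity. Both differences push the third culture towards negative in the CXL arm only. The size depends on the number of delayed eyes, which is not given.

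**The case against.** The strongest reply is that the dilution needs the less natural reading. Protocol 1.1 expects negative cultures immediately after the procedure, 3.4 treats a scrape before CXL as the result of a theatre delay, 3.5 has one visit for procedure and repeat culture, and 4.2.2 puts the scrape after CXL. All of this points to completion by the limit. The 3 h and 4 h for bacterial ulcers can also be reconciled as theatre by 3 h and completion by 4 h. This stands. What remains is that the text never says completion, that a completion limit at the scrape time leaves no minutes for transfer, and that CLAIR II has no counterpart to the 3 h.

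A second reply is that the protocol already handles early scrapes: fixed scrape time in both arms, intention to treat, and a third culture. This also stands, and those features are sound. They are written for theatre delays, though, and do not cover an on-schedule eye in mid-procedure at the scrape time.

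Third, the size is assumed. Nothing supports evenly spread starts, and the figures ignore the power that the SAP expects to gain from the baseline culture. That is correct; they are illustrations only.

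On the SAP wording, Protocol 1.2 already makes the timed culture primary, and a before/after cross-linking description fits no control eye whatever the window. So this is a separate wording problem. It should be settled in the SAP, which is the document the analyst will follow.

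**Conclusion.** The point holds as a minor one. The CXL limit should sit before the scrape, not on it, and the SAP should name the culture it analyses. The illustrated cost in CLAIR II is about 4 points of power (80% to 76%), or 2 points if the affected eyes keep half the effect. It assumes a start limit, evenly spread starts, 80% design power and pooled groups of 55. In CLAIR I the cost is nil if theatre start by 3 h is met.

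Three stronger readings are not supported:

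- A reader might infer that the window biases the trial in favour of CXL. With the timed culture and intention to treat it does the reverse. Only substituting the third culture would favour CXL, and the documents do not say that this is intended.
- A reader might apply evenly spread starts up to 4 h to CLAIR I, giving d = 1/4 and power of 57.5%. That sets aside the 3 h in Protocol 3.3 and is an outer bound, not an estimate.
- A reader might infer that scraping before CXL was overlooked. Protocol 3.4 plainly foresees it for theatre delays.

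**What to change.** **Protocol 3.3, 3.4 and 4.2.2**, one rule: *CXL is to be completed before the timed scrape; it starts no later than 3 h (CLAIR I, earlier where transfer time requires) or 22 h (CLAIR II) after enrolment.* The 22 h matches the 2 hours that Protocol 3.5 allots to the procedure and repeat-culture visit. Keep the scrape at 4 h and 24 h in both arms, including after a theatre delay, and keep intention to treat.

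**SAP section 2**, for each trial in its own paragraph: define the follow-up culture as *the repeat culture taken at 4 h (CLAIR I) / 24 h (CLAIR II) from enrolment in every randomised eye*. Keep the baseline culture in the analysis. Add: *the third culture in delayed eyes is reported separately and never replaces the timed culture.*

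**Report** the number of CXL eyes scraped before CXL was complete, so that the dilution can be judged.

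**Cost**: slightly tighter theatre scheduling (the documents give no theatre capacity or transfer time against which to test this), a protocol clarification and a short SAP edit. No extra patients, visits or procedures. True theatre delays will still occur and will still dilute the contrast.

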3.5 Study Schedule

	Visit 1	Visit 2	Visit 3	Visit 4	Visit 5
	Baseline Exam	Procedure & Repeat Culture	3-Day Repeat Culture	3 week Follow-up	Month 3 Final
Forms					
Consent and Authorization form	X				
Baseline form	X				
NEI-VFQ			X		X
Follow-up form			X	X	X
Final form					X
Procedures					
Cross-linking		X			
Tests					
IOP	X		X	X	X
Pachymetry U/S	X		X	X	X
Pentacam Topography	X				X
Slit Lamp Photography*	X			X	X
BSCVA/ETDRS/MRx		X		X	X
Total visit time	2 hours	2 hours	2 hours	1 hour	1 hour
	* Slit lamp photography also taken upon an adverse even				an adverse event

3.6 Adverse Events (AEs)

During each study visit, the subject will be questioned about AEs in a non-leading manner. All AEs, whether observed by the Investigator, elicited by the Investigator, or spontaneously reported by the subject, will be documented in the subject's chart and the adverse event form. Slit lamp photography will also be completed after any adverse event takes place.

All AEs should be followed until they are resolved or until a stable clinical endpoint is reached. Each AE is to be classified by the Investigator as SERIOUS (SAE) or NONSERIOUS (NSAE).

If a SAE occurs, the investigator at Aravind Eye Hospital, Madurai must fill out the serious adverse event form and email it to [name] at UCSF within 24 hours of the occurrence of the SAE. The investigator must provide written follow-up reports until the SAE or clinically significant AE has resolved or until a stable clinical endpoint is reached. Notification of an SAE or clinically significant AE must also be submitted to the Institutional Review Board (IRB)/Ethics Committee (EC) in accordance with its requirements. All AEs must be reported from the time that the subject provides informed consent through the last study visit.

4. PROCEDURES

4.1 Masking

Due to the nature of the intervention, the study participant, surgeon and technician performing cross-linking will not be masked, however, the physician performing repeat scraping as well as the microbiologist will be masked to treatment arm. The refractionist performing the BSCVA will also be masked. UCSF study personnel will not be given any identifying information.

4.2 Procedures

4.2.1 Corneal Gram Stain and Culture

After patient history and slit lamp examination at the enrollment visit (Day 0), corneal scraping is performed to determine the eligibility of the patient (positive fungal stain and negative bacterial stain). Corneal scraping is recommended as standard of care for all corneal ulcer patients at the Aravind Eye Hospitals. There is a small risk to patients of inducing a perforation, worsening an epithelial defect, or contaminating an ulcer, and patients are duly informed of these risks prior to the taking of the corneal scrape.

Corneal scraping will be obtained as follows:

- A drop of topical anesthetic (0.5% tetracaine or 4% lidocaine) is administered to the eye to be examined.
- Aseptic technique is used to obtain each corneal scrape. A flame-sterilized Kimura spatula is used, with the aid of slit lamp magnification, to obtain a scrape from the leading edge and base of the corneal ulcer. The Kimura spatula is again flame sterilized between the takings of each sample.
- Two scrapings are smeared directly on to two separate glass microbiology slides for Gram stain and for KOH wet mount (if necessary, Giemsa or Gram Stain can be used to identify fungal elements as well).
- Three further scrapings are taken and directly inoculated on to sheep's blood agar, chocolate agar, potato dextrose agar or Sabouraud's agar for bacterial and fungal culture.

4.2.2 Collagen Cross-Linking

All study participants randomized to collagen cross-linking will have cross-linking within 4 hours for bacterial ulcers and within 24 hours for fungal ulcers. They will be taken to the operating theatre and the procedure will be performed under sterile conditions.

Cross-linking will be performed as follows:

- A drop of topical anesthetic (0.5% tetracaine or 4% lidocaine) is administered to the eye.
- A 30-minute loading dose of 0.1% topical riboflavin and 20% dextran T500 drops will be administered every 2 minutes.
- The cornea will be exposed to UV-A light at a wavelength of 365nm with irradiance of 3mW/cm² for a total of 30 minutes.
- Throughout the UV-A treatment the study participant will continue to receive topical riboflavin Q5 min intervals during treatment.
- The study participant will be transferred back to the microbiology laboratory for repeat scraping and culture (see section 4.4.1).

4.3 Pentacam Protocol

Cornea densitometry and topography will be documented using the Pentacam HR (high resolution) Scheimpflug camera at baseline and 3 months. The images will be captured using standardized protocols by study certified ophthalmic technicians. The data will then be shared with UCSF via Dropbox.

In order to obtain the highest quality Pentacam HR Scheimpflug camera examination, the technician will scan the appropriate eye according to the Pentacam HR instruction manual.

4.3.1 Imaging Procedures

Corneal densitometry and topography measurement

- The examination will be performed in a designated diagnostic room with a uniform ambient light level.
- To begin the corneal densitometry measurement, the technician will select the examination scan for cornea densitometry measurement, per the Pentacam HR manual.
- The cornea densitometry measurement will consist of a measurement protocol of 25 images under the examination mode of 3D scan.

4.3.2 Check Scan Quality

- If Quality Specifications ("QS") field reads "OK," then the measurement is correct and reproducible.
- If the "QS" field is highlighted YELLOW, the examination will be repeated until an "OK," reading is obtained.
- If the "QS" field is RED, then the examination must be repeated.
- If an "OK" reading is not obtainable, then the best of 3 examinations will be saved.

4.3.3 Saving Image

- Download data to excel or save to USB drive
- De-identify data
 - Patient names or any other identifying information such as birthday should not appear within any of the image files.
- Rename data
 - The image files will be designated with: 1) the eye ID number, 2) the timing of visit '3m', '6m', or '12m' respectively for the 3, 6, and 12-month follow-up visits, and 3) image number of the series. An image renamed to C101_3m_1.jpg will be the first image for eye number C101's 3 month follow-up visit. An image renamed to C222_12m_3.jpg will be the third image for eye 222's 12 month follow-up visit.
- Batch upload images to Dropbox. Procedures for uploading images to Dropbox:
 - Nagivate to Dropbox → eye's folder → relevant study visit
 - Upload images to the eve's relevant study visit folder

5. STUDY MEDICATIONS

5.1 Medical management protocol & Treatment Schedule

All study participants will receive the same medical management in the initial 3 day study period. **Table 2** outlines the dosing schedule for medications for CLAIR I and CLAIR II. Study participants will be randomized to medical management plus CXL versus medical management alone. This study requires 5 visits over 3 months including baseline visit, procedure visit, 3-day follow-up, 1 and 3-month follow-up. After the 3-day repeat culture visit additional treatments may be added per clinician preference including but not limited to topical and oral antimicrobials.

Table 2: Dosing schedule for Medications in the first 3 days.

	CLAIR I	CLAIR II
Moxifloxacin 0.5%	Q 1 hours x 3 days	
Natamycin 5%		Q 1 hour x 3 days*
Amphotericin 0.15%		Q 1 hour x 3 days*
Homatropine	TID x 3 days	TID x 3 days

^{*50%} randomized to Natamycin 5% and 50% randomized to Amphotericin 0.15%

5.2 Possible Side Effects of Study Medications

Amphotericin: eye irritation, swelling, pain and/or redness, discharge

Homatropine: eye irritation, swelling, pain, or redness; Eye dilation may result in temporary blurred vision, light sensitivity, and increased heart rate.

Moxifloxacin: eye irritation, swelling, pain, or redness

Natamycin: eye irritation, swelling, pain and/or redness, discharge

6. PROTECTION OF HUMAN SUBJECTS

6.1 Institutional Review Board Approval

6.1.1 Aravind Eye Hospital, Ethics Review Committee The Ethics Committee with review the study protocol annually for ethical approval.

6.1.2 University of California, San Francisco Committee on Human Research (CHR) The UCSF CHR will review the study protocol annually for ethical approval.

6.2 Informed Consent

Aravind personnel will obtain full written consent from each patient. The primary surgeon will screen participants and determine their eligibility. He/she will clearly explain the process and risks involved and will also ask the patient to sign any necessary consent documents. The study participant will have 4 visits total per eye included in the study over 3 months; visits include hospitalization for the first 3 days and a procedure visit. The patient has the

ability to withdraw at any time and will not be forced into anything with which he/she is not comfortable. Consent documents have been uploaded to the IRB application.

